9.6 Pharmacodynamics

Not applicable.

9.7 Pharmacogenomics

Not applicable.

9.8 Biomarkers

Not applicable.

9.8.1 Additional Research Collection

This protocol will not include sample collection and/or residual sample storage for additional research (AR).

9.9 Health Economics OR Medical Resource Utilization and Health Economics

Health Economics/Medical Resource Utilization and Health Economics parameters will not be evaluated in this study.

10. STATISTICAL CONSIDERATIONS

10.1 Sample Size Determination

This is an estimation study. A sample size of approximately 8 participants will provide two-sided 95% confidence interval half-widths of 1.12, 8.93, and 136.63, respectively, for Cmax (ng/mL), AUC(TAU) (ng*h/mL), and CLT/F (mL/min) based on 80% coverage probability and historic standard deviations. These calculations are based on one-sample t-tests using historic standard deviations of 1.13, 9.03, and 138.1, respectively, for Cmax, AUC(TAU), and CLT/F, based on population PK modeling from participants with HBV following 14 days of oral 0.5 mg Baraclude

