2. SCHEDULE OF ACTIVITIES

Table 2-1: Screening Procedural Outline (AI463528)

Procedure	Screening Day -21 Visit	Notes
Eligibility Assessments		
Informed Consent	X	A participant is considered enrolled only when a protocol-specific informed consent is signed.
Inclusion/Exclusion Criteria	X	
Medical History	X	Include any toxicities or allergy related to previous treatments.
Safety Assessments		
Physical Examination (PE)	X	If the screening PE is performed within 24 hours prior to dosing on Day 1, then a single exam may count as both the screening and pre-dose evaluation.
Physical Measurements	X	Includes height, weight, and BMI.
Vital Signs	X	Includes body temperature, respiratory rate, seated blood pressure, and heart rate. Blood pressure and heart rate should be measured after the participant has been resting quietly for at least 5 minutes. Consider alternate position(s) for vital sign collection.
Concomitant Medication Use	X	
Electrocardiogram (ECGs)	X	ECGs should be recorded after the participant has been supine for at least 5 minutes.
Laboratory Tests		
Serology	X	Includes hepatitis C antibody, HIV-1 and -2 antibody, and CrCl.
Pregnancy Test	X	For WOCBP only. Urine or serum.
Serum creatinine	X	
Adverse Event Reporting		
Monitor for Serious Adverse Events		All SAEs must be collected from the date of participant's written consent until 30 days after discontinuation of dosing or participant's participation in the study if the last scheduled visit occurs at a later time

Table 2-2: On Treatment Procedural Outline(AI463528)

Procedure	Day 1	Study Discharge	Notes
Safety Assessments			
Physical Examination (PE)	X		
Physical Measurements	X		Weight only
Vital Signs	X		Includes body temperature, respiratory rate, and seated blood pressure, and heart rate. Blood pressure and heart rate should be measured after the participant has been resting quietly for at least 5 minutes. Consider alternate position(s) for vital sign collection.
Concomitant Medication Use	X		
Adverse Event Reporting			
Monitor for Adverse Events and Serious Adverse Events	X	X	See note in screening procedures.
Pharmacokinetic (PK) Assessments			
Serial Blood PK Sampling	X	X	See Section 9.5 .
Clinical Drug Supplies			
Study Drug Administration	X		Supplied by the participant.

Abbreviations: D=Day

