5.2 Number of Participants

Approximately 8 participants will be enrolled.

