6.1 Inclusion Criteria

1) Signed Written Informed Consent

- a) Informed consent forms voluntarily signed by participants including consent for screening procedures to confirm eligibility shall be obtained prior to their enrollment in the study

2) Type of Participant and Target Disease Characteristics

- a) Participants with chronic hepatitis B (CHB) (excluding participants with a superinfection) who have been confirmed to have CHB by one of the following:
 - i) Detectable HBsAg at screening and for at least 24 weeks prior to screening or detectable HBsAg for < 24 weeks and negative for IgM core antibody and confirmation of chronic hepatitis on liver biopsy
 - ii) Documentation of positive Hepatitis e antigen (HBeAg) status at screening and at least once \geq 4 weeks prior to screening

- b) Participants whose condition is stable in the investigator's judgement
- c) Participants who are being treated with 0.5 mg daily Baraclude for a minimum of 10 consecutive days prior to the study enrollment
- d) Creatinine clearance is > 50 mL/min
- e) Body mass index (BMI) of 18.5 to 30 kg/m² (BMI = body weight [kg]/height [m]²)

3) Age and Reproductive Status

- a) Males and Females, ages 20 or age of majority to 70 years, inclusive
- b) Women of childbearing potential (WOCBP) must have a negative serum or urine pregnancy test (minimum sensitivity 25 IU/L or equivalent units of HCG) during the screening period.
- c) Women must not be breastfeeding
- d) Women of childbearing potential (WOCBP) must agree to follow instructions for method(s) of contraception for the duration of treatment with study treatment(s), Baraclude, plus 5 half-lives of study treatment Baraclude (5 days) plus 30 days (duration of ovulatory cycle) for a total of 35 days post-treatment completion
- e) Males who are sexually active with WOCBP must agree to follow instructions for method(s) of contraception ([Appendix 4](#)) for the duration of treatment with study treatment(s), Baraclude, plus 5 half-lives of the study treatment (5 days) plus 90 days (duration of sperm turnover) for a total of 95 days post-treatment completion. In addition, male participants must be willing to refrain from sperm donation during this time.
- f) Azoospermic males are exempt from contraceptive requirements. WOCBP who are continuously not heterosexually active are also exempt from contraceptive requirements, and still must undergo pregnancy testing as described in this section.

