7.2 Method of Treatment Assignment

Enrolled participants, including those not dosed, will be assigned sequential participant numbers starting with 00001 (eg, 00001, 00002, 00003.... 00010). Those enrolled participants meeting inclusion and exclusion criteria will be eligible to be dosed and undergo PK sampling.

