10.2 Populations for Analyses

For purposes of analysis, the following populations are defined:

Population	Description
Enrolled Participants	All participants who sign informed consent
Treated Participants	All participants who take at least 1 dose of study treatment.

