6.3 Populations for Analyses

The following analysis populations are defined for this study:

- Enrolled participants: Participants who signed an informed consent form. This cohort will be primarily used for all listings, unless specified otherwise.
- Treated participants: Enrolled participants who receive at least one dose of study treatment (Baraclude) administered on Day 1 at the clinic. This cohort will be used to summarize demographics and safety.
- PK participants: Treated participants who have available PK concentration-time data. This cohort will be used for all PK listings.
- Evaluable PK participants: PK participants who have adequate PK profile (see [Section 8.1.4](#)). This cohort will be used to summarize PK concentrations and PK parameters.

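### Do the wrongly labelled 80% and the unspecified population of 8 undermine the precision statement for n = 8?

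*Protocol*

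**What the plan says.** Protocol 10.1 calls this an estimation study and states: "A sample size of approximately 8 participants will provide two-sided 95% confidence interval half-widths of 1.12, 8.93, and 136.63" for Cmax, AUC(TAU) and CLT/F, "based on 80% coverage probability and historic standard deviations". The historic standard deviations are 1.13, 9.03 and 138.1, and the calculation is attributed to one-sample t-tests. SAP 5 repeats the statement.

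The recruitment target is in Protocol 5.2 and the synopsis: "Approximately 8 participants will be enrolled". On who counts as enrolled:

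- Protocol Table 2-1: "A participant is considered enrolled only when a protocol-specific informed consent is signed".
- Protocol 10.2, Enrolled Participants: "All participants who sign informed consent".
- SAP 6.3: "Enrolled participants: Participants who signed an informed consent form".
- Protocol 7.2: "Enrolled participants, including those not dosed, will be assigned sequential participant numbers", with a numbering example that runs to 00010.
- Protocol 6.1, criterion 1a: consent, including consent for screening procedures, "shall be obtained prior to their enrollment in the study".

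Protocol 10.2 defines only the enrolled and treated populations, and Protocol 10.3 leaves the selection of participants for analysis to the SAP. SAP 6.3 then defines Evaluable PK participants and assigns the PK summaries to them. SAP 8.1.3 allows whole concentration-time profiles to be excluded.

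**The concern.** The precision statement is the only reason given for n = 8, and it looks faulty in two ways.

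First, a 95% confidence interval has 95% coverage. A sentence that gives 95% intervals and then an 80% coverage probability contradicts itself if read literally. A reader might suspect that the half-widths were computed at the wrong confidence level.

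Second, the half-widths depend on how many profiles are analysed, yet neither sample size section names the population. The target counts enrolled participants, which by the formal definitions means anyone who signed consent, dosed or not. If screen failures counted toward 8, or if a profile were excluded, fewer than 8 would be analysed and the 80% would no longer hold. The consent criterion in Protocol 6.1 adds doubt, because it places consent before enrolment and so suggests a narrower group.

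If both points had force, the study's stated precision would be mislabelled and not secured.

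**Working it through.** **Inputs.** n = 8, two-sided 95%, the 80% figure, and SDs of 1.13 (Cmax), 9.03 (AUC(TAU)) and 138.1 (CLT/F), all from Protocol 10.1 and SAP 5.

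**1. Reproduce the printed figures.** The half-width that a 95% t-interval stays within with 80% probability is

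h = t(0.975, n−1) × SD/√n × √[χ²(0.80, n−1)/(n−1)].

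At n = 8, t(0.975, 7) = 2.3646 and χ²(0.80, 7) = 9.8032, so the multiplier of SD is 2.3646/√8 × √(9.8032/7) = 0.83602 × 1.18341 = 0.98936.

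- Cmax: 0.98936 × 1.13 = 1.118 (printed 1.12)
- AUC(TAU): 0.98936 × 9.03 = 8.934 (printed 8.93)
- CLT/F: 0.98936 × 138.1 = 136.63 (printed 136.63)

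All three agree to rounding.

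**2. Rule out other readings at n = 8.**

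| Reading | Cmax | AUC(TAU) | CLT/F |
|---|---|---|---|
| 95% t-interval at the historic SD | 0.945 | 7.549 | 115.45 |
| 95% normal interval | 0.783 | 6.257 | 95.70 |
| 80% confidence interval, t(0.90, 7) × SD/√8 | 0.565 | 4.517 | 69.09 |
| 80% probability on width, given that the interval contains the mean | 1.127 | 9.009 | 137.78 |
| Difference detectable at 80% power, one-sample t-test | 1.306 | 10.439 | 159.65 |
| **80% probability on width, unconditional** | **1.118** | **8.934** | **136.63** |

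Only the last row matches all three printed values, so the 80% belongs to the width of the interval. In 400,000 simulated normal samples of 8, the interval contained the mean in 95.0%, and its half-width was within 0.98936 SD in 80.1%.

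**3. How much depends on 8 being the analysed number.** The probability of meeting the printed half-widths is P[χ²(n−1) ≤ (n−1) × (0.98936 × √n / t(0.975, n−1))²]. For n = 7 the bound is 6 × (0.98936/0.92485)² = 6.866, which gives 0.667.

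| Analysed n | Half-width held with 80% probability (Cmax, AUC(TAU), CLT/F) | Probability of meeting the printed half-widths |
|---|---|---|
| 6 | 1.432, 11.442, 174.99 | 51% |
| 7 | 1.248, 9.974, 152.54 | 67% |
| 8 | 1.118, 8.934, 136.63 | 80% |
| 9 | 1.020, 8.150, 124.65 | 90% |
| 10 | 0.943, 7.534, 115.22 | 95% |

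If the observed SD equals the historic one, 7 profiles give 1.045, 8.351 and 127.72, still inside the printed values.

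**4. Compare the uses of enrolled.** Protocol Table 2-1, Protocol 10.2 and SAP 6.3 all equate it with signed consent, and Protocol 7.2 is consistent with that because it includes people not dosed. Protocol 6.4 separates consenting from being entered, which is a different word for a later step. Protocol 5.4 states an expectation that enrolled participants will be at steady state; it does not redefine the term. Criterion 1a in Protocol 6.1 is the one real tension, and it sets an order of events without offering a second definition.

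**5. Find where the printed half-widths are used.** Protocol 10.3.3 lists n, means, SD, coefficient of variation, median and range. SAP 7.1 and 7.7.2 list the same kind of summaries. None of these includes a confidence interval, and no success criterion or other decision refers to the half-widths.

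**The case for a change.** The best case for acting is that the precision statement is the sole basis for n = 8, its probability is misnamed in both documents, and a reader must work backwards through the formula to learn what is claimed. Losing one profile costs about 13 percentage points (80% to 67%), whole-profile exclusion is foreseen in SAP 8.1.3, and the supplied text gives no allowance, replacement rule or minimum evaluable number. Rewording one sentence in two places would settle the label and the population.

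Part of this stands. The term is wrong in both places, and adding the word evaluable beside the 8 would be clearer. The rest has less force:

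- The sentence already fixes the confidence level at 95%, so the 80% cannot be that level, and the printed SDs and half-widths identify its meaning.
- The missing PK population in Protocol 10.2 is delegated to the SAP by Protocol 10.3, and SAP 6.3 supplies it.
- No shortfall is shown. The target is approximate, the numbering example reaches 00010, and the text of SAP 8.1.4 on adequate profiles was not available for this review, so nothing can be inferred from its absence.
- Harmonising enrolled could do harm. Adopting a narrower sense would alter the cohort that SAP 6.3 uses for most listings and that SAP 7.3.1 uses for pre-treatment status. It would also need matching edits in the synopsis and SAP 2.2.

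**Conclusion.** No change to the plan is needed. The label is a clerical error: the half-widths are correct as 80%-probability bounds on a 95% interval from 8 analysed profiles, and none of the printed numbers would change. The unstated population is a missing detail that SAP 6.3 resolves for the analysis itself, since the PK summaries come from Evaluable PK participants whatever the wording of the sample size sections. The mixed use of enrolled comes down to one criterion that sits awkwardly beside definitions that otherwise agree.

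The sensitivity is real but has no consequence here. With 6 to 10 analysed profiles the probability of meeting the printed half-widths runs from about 51% to 95%. The planned PK summaries in the supplied text report no interval and no decision uses the bound, so neither the results nor their interpretation would differ. If the documents are revised for another reason, the 80% could be described as the probability that the half-width is not exceeded.

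This rests on normally distributed PK values with the historic SDs, as the plan's own calculation assumes, and on the supplied text of the SAP, in which sections 7.7.1 and 8.1.4 could not be read. The documents give no loss rate, so no expected number of evaluable participants is derived.

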10.2 Populations for Analyses

For purposes of analysis, the following populations are defined:

Population	Description
Enrolled Participants	All participants who sign informed consent
Treated Participants	All participants who take at least 1 dose of study treatment.

10.3 Statistical Analyses

The statistical analysis plan will be developed and finalized before database lock and will describe the selection of participants to be included in the analyses, and procedures for accounting for missing, unused, and spurious data. Below is a summary of planned statistical analyses of the primary endpoint.

10.3.1 Efficacy Analyses

Not applicable.

10.3.2 Safety Analyses

Not applicable.

10.3.3 Pharmacokinetic Analyses

Individual pharmacokinetic parameter values will be derived from plasma concentration versus time using non-compartmental methods. Values will be summarized with univariate statistics (n, arithmetic mean, standard deviation, geometric mean, coefficient of variation, median, minimum, maximum). Parameters will include: Cmax, Ctrough, C24, Tmax, AUC(TAU), and CLT/F.

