5. SAMPLE SIZE AND POWER

This is an estimation study. A sample size of approximately 8 participants will provide two-sided 95% confidence interval (CI) half-widths of 1.12, 8.93, and 136.63, respectively, for C_{max} (ng/mL), $AUC(TAU)$ (ng*h/mL), and CL/F (mL/min) based on 80% coverage probability and historic standard deviations. These calculations are based on one-sample t-tests using historic standard deviations of 1.13, 9.03, and 138.1, respectively, for C_{max} , $AUC(TAU)$, and CL/F , based on population PK modeling from participants with HBV following 14 days of oral 0.5 mg Baraclude.

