7.1 General Methods

Listings display all data regardless of study period by participant and visit (if applicable). Continuous variables will be summarized using univariate statistics, i.e., number of participants, mean, standard deviation (SD), median, minimum and maximum. Geometric mean and coefficient of variation (%CV) will also be presented for continuous plasma PK parameters. Categorical variables will be summarized using counts and percentages.

Where appropriate, baseline is defined as the last non-missing result with a collection date-time less than the date-time of the first dose of study medication.

AEs will be coded using the most recent version of the Medical Dictionary for Regulatory Activities (MedDRA) in production. Non-study medications will be coded using the BMS World Health Organization (WHO) Drug Dictionary.

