7.7.2 Pharmacokinetic Parameters

The following Baraclude PK parameter values will be summarized as continuous variables: C_{max} , T_{max} , C_0 , C_{24} , $AUC(TAU)$, and CL/F .

Baraclude PK parameter values will be listed, including any exclusions and reasons for exclusion in the statistical summary.

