8.1.3 Treatment of Outliers

Individual plasma concentrations, if deemed to be anomalous, may be excluded from the analysis following a review of available documentation (e.g., bioanalytical report, clinical data). Any such exclusion will be clearly listed in the study report along with justification for exclusion.

Entire plasma concentration-time profiles for a participant may be excluded following review of available documentation (e.g., bioanalytical report, clinical data). However, results of analysis with and without the excluded profiles may be presented in the study report. Any such exclusion will be clearly listed in the study report along with justification for exclusion.

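### Must a study sized on 95% confidence-interval half-widths name a confidence interval among its planned pharmacokinetic summaries?

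*Protocol*

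**What the plan says.** Protocol 10.1 and SAP 5 give the same sample-size argument. The SAP opens it with "This is an estimation study", and the protocol states: "A sample size of approximately 8 participants will provide two-sided 95% confidence interval half-widths of 1.12, 8.93, and 136.63". The three figures are for Cmax (ng/mL), AUC(TAU) (ng*h/mL) and apparent clearance (mL/min; CLT/F in the protocol, CL/F in the SAP). They rest on historic SDs of 1.13, 9.03 and 138.1 and a probability of 80%. There is no hypothesis, margin or power statement.

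For the analysis, protocol 10.3.3 says: "Values will be summarized with univariate statistics (n, arithmetic mean, standard deviation, geometric mean, coefficient of variation, median, minimum, maximum". SAP 7.7.2 says: "The following Baraclude PK parameter values will be summarized as continuous variables". SAP 7.1 defines such a summary as number of participants, mean, SD, median, minimum and maximum, and adds: "Geometric mean and coefficient of variation (%CV) will also be presented for continuous plasma PK parameters". SAP 7.7.2 also plans a listing of the individual parameter values.

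On who is analysed, SAP 6.3 says of the evaluable PK participants: "This cohort will be used to summarize PK concentrations and PK parameters". SAP 8.1.3 adds: "Entire plasma concentration-time profiles for a participant may be excluded following review of available documentation".

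None of these sections names a confidence interval as an output. In the readable SAP, an interval appears only in Section 5.

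**The concern.** In an estimation study, precision takes the place that power holds in a comparative trial. Here the whole case for the sample size is an interval width, and the only objective is to describe steady-state pharmacokinetics. A reader would expect the analysis section to name the same interval, on the same scale, for the same three parameters. It does not, so the sizing and the analysis seem to be out of step.

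Two things could be at stake. First, a report that follows the plan to the letter might print no measure of precision for the mean. Second, the planned half-widths apply to 8 analysed participants, whereas the summaries use evaluable profiles only and whole profiles may be dropped. The achieved precision could then be worse than planned, with nothing in the table to say so directly.

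**Working it through.** **Inputs.** n = 8, the 95% two-sided level, the 80% probability and SDs of 1.13, 9.03 and 138.1 come from protocol 10.1 and SAP 5. The planned statistics come from protocol 10.3.3, SAP 7.1 and SAP 7.7.2.

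**Step 1: reproduce the stated half-widths.** For a one-sample t interval on the untransformed mean, the half-width that is not exceeded with 80% probability is

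t(0.975, n−1) / √n × √(χ²(0.80, n−1) / (n−1)) × SD.

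At n = 8, t(0.975, 7) = 2.3646, so t/√8 = 0.8360. The second factor is √(χ²(0.80, 7)/7) = 1.1834.

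| Parameter | Calculation | Result | Stated |
|---|---|---|---|
| Cmax | 0.8360 × 1.1834 × 1.13 | 1.118 | 1.12 |
| AUC(TAU) | 0.8360 × 1.1834 × 9.03 | 8.934 | 8.93 |
| CLT/F | 0.8360 × 1.1834 × 138.1 | 136.63 | 136.63 |

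All three agree. Neither a normal-quantile interval (0.783, 6.26, 95.7) nor a t interval without the 80% factor (0.945, 7.55, 115.5) gives the stated figures. The interval behind the sizing is therefore identified without doubt: a t interval for the arithmetic mean.

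**Step 2: can that interval be had from the planned output?** It is mean ± t(0.975, n−1) × SD/√n. Its only ingredients are n, arithmetic mean and SD, and both documents plan all three. At n = 8 the half-width is 0.8360 × the reported SD.

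**Step 3: can the planned table be set against the planning figures?** Divide each stated half-width by 0.8360:

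- Cmax: 1.12 / 0.8360 = 1.34 ng/mL
- AUC(TAU): 8.93 / 0.8360 = 10.68 ng*h/mL
- CLT/F: 136.63 / 0.8360 = 163.4 mL/min

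A reported SD at or below these values means that the planned precision was reached at n = 8. For another n, only the multiplier changes: t/√n is 0.9248 at n = 7 and 1.0494 at n = 6. Since n is the first statistic in the planned table, the reader knows which multiplier to use.

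**Step 4: does rounding spoil this?** SAP 8.1.1 reports the SD to one decimal more than the mean. Under its coarsest rule (mean of 100 or more, so SD to one decimal), the rounding error in the half-width at n = 8 is at most 0.8360 × 0.05 = 0.042 in the parameter's own units. For CLT/F that is negligible against 136.63, and it would be small even against 8.93 for AUC(TAU). For Cmax, if the mean is near the 4.2 ng/mL that protocol 3.2.4 gives for healthy subjects, the SD is printed to three decimals and the error is at most 0.8360 × 0.0005 = 0.0004.

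**Step 5: would adding the interval change any number?** No. The means, SDs, sample size and set of evaluable participants are the same with or without the extra column.

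**The case for a change.** The best case for a change is that precision is the one thing the study was sized to deliver, and that committing to report it would cost a sentence. On the readable text the mismatch is real, and that part stands.

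A second argument is that the half-widths hold only for 8 evaluable profiles. With the planning SDs and normal data, the chance of meeting them falls from 80% at n = 8 to 67% at n = 7 and 51% at n = 6 (7 and 6 are assumed numbers). These figures are correct, but they measure the loss of participants. They would be identical with a printed interval, so they do not show harm from its absence. SAP 8.1.3 also requires any exclusion to be listed with its justification.

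A third argument concerns the geometric mean. The readable text does not say whether the %CV is arithmetic or geometric, and no log-scale SD is listed, so a log-scale interval may not follow from the summary table. That is so. But the sizing makes no claim on the log scale, and the individual values of about 8 participants are to be listed, from which such an interval can be computed.

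There are also limits to what the public text can show. Protocol 10.3 presents its analysis sections as a summary and leaves the detail to the SAP. SAP 8 and 9 refer to the sponsor's table standards and to a Data Presentation Plan. SAP 7.7.1 and 8.1.4, those standards and the table templates cannot be read here. An interval may be specified in one of them.

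**Conclusion.** No change to the plan is needed. The sample-size section relies on a t-based 95% interval for the arithmetic mean, and the readable analysis sections do not name it. That is a gap in presentation, not in information. The interval is fully determined by three statistics that are already planned, and the comparison with the sizing needs one multiplication: 0.836 × SD at n = 8, against 1.12, 8.93 and 136.63.

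Nothing turns on whether the interval is printed. No test, margin or success criterion uses it, the estimates are unbiased or biased to the same degree either way, and the sample size is unaffected. Only the sample size rests on the half-widths; the reason for doing the trial is the lack of pharmacokinetic data in Japanese patients (protocol 3.1). An analyst who adds the interval to the table does something sensible that the present wording does not prevent, and amending the protocol for it would bring no gain.

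This conclusion assumes that n, mean and SD are reported for each parameter as planned, with n being the number actually analysed. The 80%, 67% and 51% figures further assume normal data and the historic SDs.
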